## 7. TRIAL PARTICIPANTS

### 7.1 Overall Description of Trial Participants

- 1) Participants with mild-moderate AzD
- 2) Participants with MCI
- 3) Healthy older adults
- 4) Post-ischaemic stroke

### 7.2 Inclusion Criteria

Study specific inclusion criteria will be as follows:

One of:

- 1) Healthy controls will be free of any medical co-morbidity or medication that could adversely affect cognition. Volunteers with well-controlled co-morbidities (i.e. hypertension, diabetes, will be considered for inclusion)
- 2) MCI as defined by NIA/AA 2011 and Petersen criteria
- 3) AzD as defined by the NIA/AA 2011 criteria
- 4) Ischaemic stroke within the last 12 months

And:

- 5) Deficits will be mild to moderate as defined by Montreal Cognitive Assessment (MoCA) score of  $>/=9$  for all participants with MCI or Alzheimer's disease (32-34).
- 6) Willing to participate
- 7) Capacity to consent to the study/personal consultee
- 8) Patients on and off anti-dementia medications will be included (acetylcholinesterase inhibitors, glutamate receptor antagonists)
- 9) Good understanding of written and spoken English
- 10) Age  $>50$  years (MCI, AzD, and healthy controls only)
- 11) Access to the internet and a computer or laptop.

### 7.3 Exclusion Criteria

Study specific exclusion criteria as follows:

- 1) Healthy controls with any medical co-morbidity or medication that could adversely affect cognition, or poorly controlled medical co-morbidities (i.e. hypertension, diabetes)
- 2) Unwilling to take part
- 3) Unable to consent/no personal consultee
- 4) Major medical co-morbidity; severe heart failure (ejection fraction <20%), significant carotid artery stenosis >50%), severe respiratory disease, major stroke (MCI and AzD groups only)
- 5) Pregnancy, planning pregnancy, or lactating
- 6) Inadequate bilateral TCD windows
- 7) Participants already enrolled into other interventional studies
- 8) Insufficient understanding of written and spoken English
- 9) Age <50 years (MCI, AzD, and healthy controls only)
- 10) No access to the internet and a computer or laptop.

## 8. STUDY PROCEDURES

### 8.1 Participant identification

This study has broad recruitment strategy to ensure that recruitment targets are met. Our previous pilot study, and other dementia studies have demonstrated that this is the most appropriate recruitment strategy. Appendix A outlines the participant recruitment pathway for this study. Appendix B outlines the overall study flow process, and Appendix C outlines the schedule of procedures for each participant.

#### Healthy volunteer identification

Healthy volunteers will be recruited through poster advertisement at the University of Leicester, University Hospitals of Leicester (UHL), LPT, and GP surgeries, and pharmacies in the East Midlands. In addition, healthy volunteers will be recruited from friends, family, and carers of enrolled patient participants, and through the healthy volunteer section of Join Dementia Research (see below). In addition, the University of Leicester holds a research interested list of healthy volunteers who will be contacted by the researcher to provide study specific information if they are interested in participating. Interested participants will self-refer directly to the researcher who will provide study specific information. Participants will be allowed a minimum of 24 hours to decide if they would like to enrol in the study, and to contact the researcher who will arrange for them to undergo an eligibility assessment (see Section 8.2) and the formal consent (Section 8.3) and study enrolment.

#### Patient identification

##### Secondary care services - geriatric and memory service recruitment

Eligible participants will be identified by Consultants and specialist registrars in Geriatric Medicine, or Old Age Psychiatry, or specialist nurses from the memory service, by screening their medical records for the inclusion and exclusion criteria. Eligible participants will be approached by the above members of the direct care team and referred to the researcher or research delivery team for further information. In addition, screening of eligible participants under the geriatric and memory service will be undertaken by research delivery officers from the NIHR CRN, UHL, and LPT, and eligible participants that are interested will be approached by a member of their direct care team, and if interested referred to the researcher or research delivery team and provided with study specific information.

#### Research interested list

The LPT hold a research interested list of patients whom they may approach if they are eligible for the study. Research delivery staff at the LPT will eligibility screen the list and contact participants who meet the inclusion and exclusion criteria. Interested participants will then be provided with study specific information by the LPT research delivery team.

#### Primary care recruitment

A database search will be conducted with the support of the NHR CRN for GP surgeries in Leicester and Leicestershire. Eligible participants will be screened from the database by a member of the direct care team at that practice. Participants that meet the inclusion and exclusion criteria will be invited to join the study through letter invitation from their GP surgery. Participants who contact the researcher or research delivery officer after letter invitation will then be provided with study specific information by the research team.

#### Community group recruitment

Study specific information will be provided to attendees at local community groups (i.e. Alzheimer's society memory café) by volunteers and the members of the research team. In order to eligibility screen the interested participants, a referral will be made to their GP practice or LPT research delivery team (depending on participant location) to check eligibility prior to study recruitment. This will be prior to consent and will be limited to the GP practice or LPT research delivery team confirming to the researcher that the participant meets the inclusion and exclusion criteria to enrol in the study.

#### Join Dementia Research recruitment

Join Dementia Research is an online platform that patients with dementia can access to register their interest in dementia research studies. Participants upload information to allow researchers to screen their medical history to check for study eligibility prior to contacting them. JDR provides formal training to researchers using JDR to recruit eligible patients. For this study, the researcher or research delivery officers will screen potential participants utilising the information provided on JDR and contact eligible

participants by their preferred contact method or chosen representative to provide study specific information.

#### Self-referral

Posters advertising the study will be displayed in the GP practices and pharmacies in the East midlands. In addition, posters will be displayed on the University of Leicester campus, and in the University of Leicester newsletter, outpatient clinics in the Geriatric and memory services at University Hospitals of Leicester and LPT. The researcher's contact details will be displayed on the poster's and leaflets. Participants can contact the researcher for further information, and if interested, a referral will be made to their GP practice or LPT research delivery team (depending on participant location) to check eligibility prior to study recruitment. This will be prior to consent and will be limited to the GP practice or LPT research delivery team confirming to the researcher that the participant meets the inclusion and exclusion criteria to enrol in the study.

Participants must be enrolled into the study and randomised to control or intervention within four to six weeks of initial screening.

#### Post stroke sub-group

Participants in the stroke sub-group will be recruited from ongoing observational studies in the department, stroke and rehabilitation wards, and stroke and TIA clinics at UHL, and stroke community groups and organisations. Potential participants will be screened and approached by a member of the direct care team, or research nurses from the NIHR CRN, in the first instance, and referred to the research team to provide study specific information. Stroke specific posters will be displayed in the stroke and rehabilitation wards, and stroke and TIA clinics at UHL. In the same manner as the main study, any participant who self refers or is identified through a community group, will be screened either by their direct clinical care team, or NIHR CRN research nurse to ensure they meet the study inclusion and exclusion criteria. Participants in the post-stroke sub-group will then undergo identical study procedures as outlined below.

#### 8.2 Eligibility visit (cognitive assessment)

##### Healthy volunteer eligibility assessment

Eligibility assessment will take place by discussion with the volunteer and researcher to confirm the inclusion and exclusion criteria, prior to provision of study specific information. Medical records will not be screened to eligibility assess healthy volunteers. Volunteers who meet the inclusion and exclusion criteria will be invited to the cerebral haemodynamics in ageing and stroke medicine (CHiASM) research space for formal consent.

#### Patient eligibility assessment

Medical records will be reviewed by the direct care team referring the participant for study inclusion, or by LPT/UHL research delivery officers to ensure they meet the inclusion and exclusion criteria prior to referral to the researcher or research delivery team and provision of study specific information. Eligibility screening will only be undertaken by the direct clinical care team for potential participants, or by research delivery officers that are authorised to do so. Members of the research team will only screen medical records to confirm medical and medication history after formal consent to the study has taken place.

In all cases, a permission to screen consent form will be undertaken to allow a Montreal Cognitive Assessment (MoCA) to take place, to ensure deficits are classified as mild to moderate to be eligible for study inclusion. Participants will be counselled that this may preclude them from enrolling in the study, and will be detailed on the permission to screen consent form.

### 8.3 Informed Consent

#### Healthy volunteer consent procedure

Participants who meet the inclusion and exclusion criteria will then be invited by the researcher to attend the CHiASM research space at UHL to undergo formal consent and the baseline assessments outlined in Section 8.3. All informed consent procedures and healthy volunteer assessments will be undertaken by the researcher.

#### Patient consent procedure

Informed consent will be undertaken by either [name] (researcher) or an appropriately qualified research delivery officer at the LPT research delivery team. This will take place in the most convenient location for the participant including; their home, memory service, dedicated research space at the LPT, or invited to the Cerebral

Haemodynamics in Ageing and Stroke Medicine (CHiASM) research space.

Both participants who have capacity, and those that lack capacity will be suitable for inclusion in this study. In cases where the participant lacks capacity, a friend, relative or carer will act as a personal consultee to consent on behalf of the participant. Please see section 14.1 for more information on the ethical code of practice for the inclusion of adults lacking capacity in this study.

The participant or personal consultee must personally sign and date the latest approved version of the informed consent form before any study specific procedures are performed.

The qualitative arm of the study will be consented alongside the feasibility RCT. All participants will be offered to take part in the qualitative arm of the study. Participants will be consented at enrolment into the RCT to be contacted at later date to discuss the option of the qualitative study. Participants that completed the RCT and all assessments will be suitable for inclusion in the qualitative study, and their carers will also be invited to participate. Qualitative study specific information will be provided by the researcher alongside information for the feasibility RCT at study enrolment.

Written and verbal versions of the participant information and Informed consent will be presented to the participants/personal consultee detailing no less than: the exact nature of the study; the implications and constraints of the protocol; the known side effects and any risks involved in taking part. It will be clearly stated that the participant is free to withdraw from the study at any time for any reason without prejudice to future care, and with no obligation to give the reason for withdrawal.

The participant will be allowed a minimum of 24 hours to consider the information, and the opportunity to question the Investigator, their GP or other independent parties to decide whether they will participate in the study. Written Informed Consent will then be obtained by means of participant or personal consultee dated signature and dated signature of the person who presented and obtained the informed consent. The person who obtained the consent will be suitably qualified and experienced, and have been authorised to do so by the Chief/Principal Investigator as detailed on the Delegation of Authority and Signature log for the study. The original signed form will be retained at the study site within the Trial Master File (TMF) or Investigator Site File (ISF). A copy of the signed Informed Consent will be given to participants and a copy retained in the participant medical notes.

#### 8.4 Baseline Assessments

Participants who meet the inclusion criteria, will undergo baseline assessments with a member of the research team, or research delivery officer, either at home, designated LPT research space, or invited to attend the CHiASM research space. The first visit will take place at the CHiASM research space, based at the Leicester Royal Infirmary, for an assessment of cognition (ACE-III) and neurovascular function (outline below). Approximately 20-25% of potential participants will have insufficient bilateral temporal windows for assessment, and this would preclude their study entry. Following successful window insonation, and completion of the neurovascular assessment, the following baseline assessments will be undertaken at the same visit or within two weeks at the participant's home: mood (GDS-15), function/ADLs (Lawton-IADL), quality of life (DEMQOL), handedness (Edinburgh handedness inventory).

An assessment of neurovascular function will take place using a protocol validated by this group previously (35). Participants will be asked to refrain from caffeine, nicotine, alcohol, heavy meals, or strenuous exercise for at least four hours prior to the neurovascular assessment. In summary, participants will undergo continuous beat-to-beat monitoring of cerebral blood flow velocity (CBFv) using transcranial Doppler ultrasound (TCD, DWL Doppler box), blood pressure (Finometer), heart rate (3-lead ECG), and end-tidal CO2 (ETCO2, capnography, nasal speculum). Participants will undergo a five-minute baseline recording. Participants will be asked five selected tasks from the ACE-III (attention, memory, language, fluency and visuospatial domains) to stimulate changes in CBFv, which can be measured by the above methods.

For the post-stroke sub-group, a further four tasks will be undertaken. The serial sevens will be completed in addition to serial 2s and 17s, and the naming words with “p” will be completed in addition to words beginning with “r” and “v”. This is to identify subtler deficits that may be present in the stroke sub-group.

Data collected on baseline demographic information will include the following:

##### Demographics

The age, sex, ethnicity, smoking status, alcohol intake, height, weight, BMI, years of education, and socioeconomic status (postcode) will be recorded.

##### Medical History

Details of any history of disease or surgical interventions in the following systems will be recorded; cardiovascular, abdominal, respiratory, neurological, and hearing and visual impairment. Data will be collected on the type, size, and location of the infarct in the post-stroke sub-group, and any complications of the infarct.

#### Concomitant Medication

All over-the-counter or prescription medication, vitamins, and/or herbal supplements will be recorded on CRFs. Medication, dose, duration, strength and frequency will be recorded.

#### 8.5 Randomisation and Codebreaking (if applicable)

Randomisation will be performed using Sealed Envelope®, by the researcher. This is an online-based randomisation tool which uses random permuted blocks to allocate participants to waiting list control or intervention. Participants will be enrolled and assigned a PIN consecutively, and randomised to a treatment arm corresponding to the PIN. Given the nature of the trial, it is not possible to blind participants to the intervention. The Investigator will be providing weekly telephone support with the intervention, in addition to undertaking baseline and follow-up measurements, and therefore blinding of the investigator is also not possible. However, data analysis will be blinded by generating a batch-anonymised data set. Randomisation will be undertaken at the initial visit. As this is an un-blinded trial, code breaking will not be required.

Once participants have been randomised to the intervention arm, they will be provided with information on how to access and use the CT program.

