## 2. SYNOPSIS

Study Title	The Cognition and Flow Study: The Effects of Brain Training on Brain Blood Flow
Internal ref. no.	0677
Trial Design	Feasibility Randomised Controlled Trial
Trial Participants	Healthy older adults, adults with mild cognitive impairment (undifferentiated), adults with mild to moderate Alzheimer's disease, adults 12 months post-ischaemic stroke.
Planned Sample Size	80 participants in total, 20 participants in each of the four sub-groups.
Follow-up duration	Three to six months
Planned Trial Period	12 -18 months
Primary Objective	The primary objective of this study is to determine the ability to carry out (feasibility) of a large scale randomised controlled trial (RCT) of cognitive training (CT) in healthy older adults (HC), and people with Alzheimer's disease (AzD), mild cognitive impairment (MCI), and people post-ischaemic stroke.
Secondary Objectives	Are there any clinical benefits of a CT program in patients with dementia and any difference between groups (MCI/AzD/healthy older adults/post-ischaemic stroke) in ability to carry out everyday activities, memory, mood, and quality of life outcomes?
Primary Endpoints	
 
1) Percentage of participants successfully recruited
 
2) Percentage of participants able to successfully complete CT program and complete all assessments
 
3) Percentage of participants with full bilateral data for CBFv
 
4) Feasibility of randomisation to waiting list control
 

Secondary Endpoints	
 
1) Change in cognition score as detected by the Addenbrooke's cognitive examination (ACE-III)
 
2) Change in functional status - Lawton Instrumental Activities of Daily Living (IADL)
 

	
3) Change in mood – Geriatric Depression Scale (GDS-15)
 
4) Change in quality of life measure – Dementia Quality of Life Measure (DEMQOL)
 
5) Change in task activation increase in CBFv from baseline

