### 5.2 Secondary Objectives

- 1) Are there any clinical benefits of a brain training program in patients with dementia and any difference between groups (MCI/AzD/healthy older adults/post-ischaemic stroke) in ability to carry out everyday activities, memory, mood, and quality of life outcomes?
- 2) Are there any changes in blood flow responses to cognitive tasks using TCD before and after brain training?
- 3) Are there any brain blood flow markers that can be used to predict who will benefit from brain training, and in which memory areas to generate a personalised training plan for individual patients?

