#### Feasibility and Baseline Demographics

Data will be reported as mean (standard deviation) for continuous variables, and number (percentage) for nominal data. Differences between the intervention and control groups will be analysed within population group (HC/AzD/MCI) using Chi-Square for nominal data, and independent t-testing for continuous data. Any differences between population groups will also be reported.

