#### Outcome Data

The difference for each participant between baseline and follow-up assessment for each of the continuous outcome measures described in Section 6.2 (secondary outcome measures) will be reported along with the overall mean difference. To assess the impact of the intervention and population group on each of these differences, a two-way ANOVA will be carried out. The interaction between population group and treatment group will also be included to assess if the difference between the treatment groups is different between the population groups.

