## 11.2 The Number of Participants

60 participants will be required to complete the programme, in three sub-groups of twenty (healthy older adults, AzD and MCI). This does not include participants who did not have adequate bilateral TCD windows, which has been listed in section 7.3 as an exclusion criterion. Authors generally agree that recruiting between 24 and 50 participants for a feasibility study is adequate and therefore the planned target of 60 participants is sufficiently large enough whilst giving a margin for drop-outs and loss to follow-up (41, 42). Given the primary aim of this study is feasibility, a formal power calculation has not been performed.

For the qualitative arm, participants will be recruited as a sub-set of those who were enrolled into the training arm of the trial. Both participants who did and did not complete the training programme will be invited for interview or focus group to better understand any issues that arose during the programme, reasons for non-adherence, or premature withdrawal. The sample size will therefore be determined by the number who were randomised to the treatment arm and are willing to return for interview or focus group. At the point at which responses to interview questions become saturated, no further participants will be recruited to the qualitative arm.

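### Section 8.5 names no stratification by population, so arm balance within each group of 20 is not guaranteed although the analysis examines the arm effect by population

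*Combined protocol and SAP*

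**What the plan says.** Section 8.5 states that the online tool "uses random permuted blocks to allocate participants to waiting list control or intervention", and then: "Participants will be enrolled and assigned a PIN consecutively, and randomised to a treatment arm corresponding to the PIN". It gives no stratification factor, allocation ratio or block size. No other section mentions stratification, minimisation or a separate list for each population.

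The Synopsis plans "80 participants in total, 20 participants in each of the four sub-groups". Section 11.2 still has "60 participants will be required to complete the programme, in three sub-groups of twenty", without the stroke group. Under Post stroke sub-group, section 8.1 says: "Participants in the post-stroke sub-group will then undergo identical study procedures as outlined below". Section 8.5 therefore applies to stroke participants too.

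Section 5.2 asks whether training brings clinical benefit and whether there is "any difference between groups (MCI/AzD/healthy older adults/post-ischaemic stroke"). Section 11.1, Outcome Data, fits a two-way ANOVA to the change scores with arm, population and their interaction, the last "to assess if the difference between the treatment groups is different between the population groups".

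**The concern.** The interaction and the population-specific arm effects depend on how many participants each arm has inside each population. Section 8.5 does not control that number, although population follows from the inclusion criteria and is known before allocation.

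With 20 per population, an even split gives 10 against 10. A chance split of 13:7 or 14:6 has three effects:

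- The interval for that population's arm effect widens.
- If the smaller arm is the trained one, only 6 or 7 people in that population inform the program-completion part of the second primary endpoint. The qualitative sample, which section 11.2 draws from the training arm, shrinks too.
- The ANOVA has unequal cells, and section 11.1 does not say how they are handled.

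Section 11.1 also uses these outcome data to size the larger trial.

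**Working it through.** **Inputs from the documents.** Four populations of 20, so 4 × 20 = 80, which matches the Synopsis. Section 11.2 has 3 × 20 = 60. There is no power calculation to reproduce.

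**Assumptions.** 1:1 allocation, blocks of 4 or 6, and a single block sequence for everyone. None of these is stated. Arrival order is also not given, so two cases are shown. The amendment history records the stroke group as added in version 5 (21/2/19), after version 1 (30/8/18), so a late-arriving stroke group is plausible.

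**Step 1. One population, all four mixed.** If 40 of 80 are trained and a population is 20 of the 80, the number trained in it is close to hypergeometric:

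SD = √[20 × 0.5 × 0.5 × (80 − 20)/(80 − 1)] = √3.797 = 1.95

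| Split in a given population | Probability |
|---|---|
| exactly 10:10 | 0.20 |
| 12:8 or worse | 0.44 |
| 13:7 or worse | 0.20 |
| 14:6 or worse | 0.07 |

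Simulation with blocks of 2, 4, 6, 8 or mixed sizes gives nearly the same values, so the unknown block size matters little when arrivals are mixed.

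**Step 2. At least one population (simulation, blocks of 4 or 6).**

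| Arrival order | 13:7 or worse | 14:6 or worse |
|---|---|---|
| All four fully mixed | about 0.52 | about 0.23 |
| Other three mixed, stroke last | about 0.35 | about 0.13 |
| Each population in turn | 0 | 0 |

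With stroke last, the stroke group itself is never worse than 11:9. Recruiting each population in turn with blocks of 4 gives 10:10 in each. No section plans recruitment in that order.

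**Step 3. Cost of a split k : (20 − k).**

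Variance ratio against 10:10 = [1/k + 1/(20 − k)] / [1/10 + 1/10]

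- 13:7: (0.0769 + 0.1429)/0.2 = 1.099. Standard error ratio √1.099 = 1.048.
- 14:6: (0.0714 + 0.1667)/0.2 = 1.190. Standard error ratio √1.190 = 1.091.
- Averaged over the distribution in step 1: 1.043. Standard error ratio √1.043 = 1.021.

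For an assumed difference of 1 SD at two-sided 0.05 (normal approximation), power within a population is 61% at 10:10, 57% at 13:7 and 54% at 14:6.

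**Step 4. Blocks stratified by population, 20 per stratum.** The worst possible split is 10:10 for blocks of 2 or 4, 11:9 for blocks of 6, and 12:8 for blocks of 8. The total stays at 80.

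**The case against.** Several points on the other side stand.

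- **A single sequence is inferred.** The text does not say how many lists there are, and the flow charts in Appendices A and B could not be seen. The inference rests on consecutive PINs and the absence of any named factor. It is the natural reading, but the tool may already be stratified.
- **The expected cost is small.** The average loss is about 4% in variance, or 2% in standard error. Ten against ten is imprecise whatever the allocation scheme. The trial's primary aim is feasibility, and section 11.2 makes no power claim.
- **The completion endpoint** in section 6.2 is not required separately for each population.

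Three stronger readings are tempting, and the documents do not support them.

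- A reader might infer that the arms will be unbalanced within populations, or that the comparison is biased. Any imbalance is by chance, allocation stays random, and the blocks preserve overall balance.
- A reader might infer that arm becomes confounded with diagnosis in the outcome analysis. The planned ANOVA is on change scores and includes population, and no pooled outcome comparison without population is specified.
- A reader might take "Differences between the intervention and control groups will be analysed within population group (HC/AzD/MCI") as the efficacy analysis. That sentence falls under Feasibility and Baseline Demographics. The efficacy contrasts are those under Outcome Data.

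The objections lower the weight of the point but do not remove it. The plan examines the arm effect by population, and section 8.5 does not protect the split on which those estimates rest.

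**Conclusion.** The point holds as a moderate design weakness. As written, section 8.5 does not guarantee balance within population, although section 5.2 and the ANOVA look at population-specific effects. Under 1:1 allocation, blocks of 4 or 6 and one sequence, the chance that at least one population is split 13:7 or worse is about 35% to 52%. For 14:6 or worse it is about 13% to 23%. The lower ends assume that stroke is recruited last, the upper ends full mixing. The affected contrast loses about 5% or 9% in standard error at those splits, and about 2% on average.

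The validity of the randomisation and the overall arm comparison are not in question. The effect is on the precision of the secondary analyses, on the number of trained participants per population, and on the estimates carried into the larger trial. Fully sequential recruitment by population would largely remove the problem, but it is not planned.

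**What to change.** Change section 8.5 to read along these lines: *Participants will be allocated 1:1 to intervention or waiting list control by random permuted blocks, stratified by population group (HC, MCI, AzD, post-stroke). Block sizes will vary and will be concealed from the researcher who randomises.* The 1:1 ratio is assumed here, and the sponsor should state the ratio actually used. Delete the sentence that ties the arm to the consecutive PIN. The ANOVA already includes population, so it would then match the randomisation.

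The change needs no extra participants or visits. It does need a protocol amendment, with the approvals listed in section 14.5. If recruitment has started, it applies only to later participants and does not repair imbalance already accrued. In that case, report the split by population and state how the ANOVA handles unequal cells. If the tool is already stratified, only the text of section 8.5 needs correcting.
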